## **5 OUTCOMES**

### **5.1 Primary outcome**

Reduction of 50% in latent TB in the treatment group after 12 months of intervention, estimated by IGRA QuantiFERON TB Gold Plus – Qiagen.

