## 6.4 Indications for premature exclusion

The participant may be withdrawn from the clinical trial at any time for the reasons listed below:

- at the request of the participant (withdrawal or withdrawal of consent);
- non-compliance with the protocol;
- interruption of treatment or sum of temporary interruptions of intervention  $\geq 90$  days, either by decision of the participant or at medical discretion;
- transfer to another prison unit or early release;
- Clinical or laboratory AE requiring permanent discontinuation of medication (according to study-specific SOP);
- any exclusion criterion according to item 5.3 that, incidentally, arises during the follow-up (both recently diagnosed and not previously recognized);
- use of acetaminophen, valproic acid, carbamazepine, cycloserine, ethionamide, corticosteroids, diazepam, triazolam, disulfiram, phenytoin, aluminum hydroxide and rifampicin which, at the discretion of the investigator, are used in a dose that may interfere with the efficacy of INH as medication;
- another reason, at the discretion of the principal investigator or study coordinator.

At the time of the participant's withdrawal, a premature exclusion visit with clinical evaluation, evaluation of AE and blood and / or sputum collection should be performed according to the clinical judgment, according to the study schedule (figure 1).

In addition, for cases in which treatment has been interrupted by decision of the participant or at medical discretion, as of 6 months from the start of the DOT, the participant will have two options: to remain in the study without the intervention (DOT), but with the accomplishment of all the visits anticipated in the protocol or to leave completely of the study without the realization of

additional collections and other accompaniments. For the latter case, follow-ups will be carried out only if the participant presents some AE at the time of their withdrawal.

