## 6.6 Estatistical analysis

Data on demographic, socioeconomic, medical and criminal history, as well as on pre, intra and post-intervention laboratory tests will be stored online at REDCap, available at <<http://www.matogrossodosul.fiocruz.br/redcap/>>, where each researcher is identified by single user and password, guaranteeing restricted and confidential access. Statistical analysis will be done with IBM® SPSS Statistics software.

The incidence will be calculated on the basis of the new cases detected during the follow-up period, per 100 person-years. It will be considered a new case of TB individuals, regardless of the group, who present bacilloscopy or positive culture. For latent TB, a seroconversion will be considered for individuals who exhibit interferon gamma levels above the upper limit considered by the manufacturer of the QuantiFERON® TB Gold Plus commercial test in the 12th or 24th month.

The effect of the intervention will be calculated through Relative Risk (RR), considering a Confidence Interval of 95% (95% CI). To determine the effectiveness of the intervention will be used Relative Risk Reduction (RRR) and Absolute Risk Reduction (RAR). In addition, to measure the impact of the intervention, the Number Needed to Treat (NNT) will be calculated.

Two protocols will be performed for statistical analysis: 1) intention-to-treat analysis and 2) per protocol. The sample calculation for the primary outcomes is based on intention-to-treat analysis.

The intent-to-treat analysis will be performed for all subjects who complete at least 6 months of treatment. The participant may decide to withdraw the consent in whole or in part. In the case of withdrawal of partial consent IGRA will be withdrawn at the 12th or 24th month and the participant will remain in the study according to the initial randomization.

Analysis by protocol will be performed only using the group of individuals who completed at least 80% of the predicted doses of the study.

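### Section 6.4 states the option to stay in follow-up off study drug only from month 6, so no month-12 IGRA is planned for participants withdrawn earlier

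*Combined protocol and SAP*

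**What the plan says.** Section 6.4 opens its list with "The participant may be withdrawn from the clinical trial at any time for the reasons listed below". The grounds include "interruption of treatment or sum of temporary interruptions of intervention" (90 days or more), "Clinical or laboratory AE requiring permanent discontinuation of medication", non-compliance, and use of certain other medicines where the investigator judges that the dose may interfere with isoniazid (INH). Transfer and early release are listed too.

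A withdrawn participant has one premature-exclusion visit, where "blood and / or sputum collection should be performed according to the clinical judgment, according to the study schedule (figure 1"). Figure 1 marks IGRA and sputum at that visit as optional.

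For treatment stopped by the participant or on medical grounds, the section then says that "as of 6 months from the start of the DOT, the participant will have two options: to remain in the study without the intervention (DOT"), attending every planned visit, or to leave with no further collections. No such choice is stated for anyone who stops before month 6.

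Three other places bear on this:

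- Section 5.1 sets the primary endpoint: "Reduction of 50% in latent TB in the treatment group after 12 months of intervention, estimated by IGRA QuantiFERON TB Gold Plus".
- Section 6.5 has everyone giving sputum and blood for IGRA at months 6 and 12, and again at month 24.
- Section 6.6 says the sample size rests on intention to treat, but limits that analysis set to participants with at least six months of treatment. On partial withdrawal of consent it refers to an IGRA at month 12 or 24 and adds that "the participant will remain in the study according to the initial randomization".

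**The concern.** The endpoint is an IGRA result at month 12. Someone who stops drug at month 7 can choose to have it measured. Someone who stops at month 2 for the same reason can be withdrawn with, at most, an optional IGRA at that time, which is not the month-12 endpoint.

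This is a matter of data collection and is separate from how Section 6.6 labels its analysis sets. If the intention-to-treat set were redefined tomorrow as all randomised, the month-12 results of participants withdrawn early would still be absent, and an all-randomised estimate would have to lean on assumptions that the data cannot test.

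The loss may be selective. Intolerance of INH is one reason to stop, and INH participants who stop early presumably lose some or all of their protection. Leaving them out compares continuing INH participants with continuing placebo participants, which is not the comparison that was randomised. The 30% added for losses protects precision; it does nothing about selective loss.

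**Working it through.** **1. The plan's own figure.** Inputs from Section 6.1.1: 20% against 10% at one year, 5% significance (two-sided assumed), 90% power. The usual two-proportion formula is n = [1.960·√(2·0.15·0.85) + 1.282·√(0.20·0.80 + 0.10·0.90)]² / 0.10² = 265.9 per arm, or 532 in total. With continuity correction, (n/4)·[1 + √(1 + 4/(n·0.10))]² = 285.5, so 286 per arm and 572 in total. The unpooled formula with the same correction gives 566. The stated 560 lies within about 2% of both corrected figures, and 560 × 1.30 = 728, or 364 per arm. The sample size is not the problem here; it supplies the 20% and 10% used below.

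**2. The passages side by side.**

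| Participant | Option to stay off drug | Planned month-12 IGRA |
|---|---|---|
| Stops from month 6 | Stated (6.4) | Yes, if the participant stays |
| Withdrawn before month 6 | None stated (6.4) | None; optional IGRA at the exclusion visit |
| Everyone, per 6.5 | Not discussed | Yes |
| Partial withdrawal of consent, per 6.6 | Kept in randomised arm | At month 12 or 24; unclear whether the six-month threshold applies |

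**3. Size, as illustration only.** The documents give no rate of stopping before month 6 and no infection risk in stoppers, so both are assumed. Let a share f of each arm stop before month 6 at average background risk. Continuing INH participants have the planned 10% and placebo 20%, so the analysed relative risk (RR) is 0.10/0.20 = 0.50. With stopper risk s on INH:

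all-randomised RR = [(1 − f)·0.10 + f·s] / 0.20

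| f | s = 20% (no protection) | s = 17.5% (stop at month 3) | s = 10% (full effect kept) | Power, 364 per arm followed, s = 20% |
|---|---|---|---|---|
| 5% | 0.525 | 0.519 | 0.50 | 94.7% |
| 10% | 0.55 | 0.5375 | 0.50 | 92.0% |
| 20% | 0.60 | 0.575 | 0.50 | 83.9% |
| 30% | 0.65 | 0.6125 | 0.50 | 72.1% |

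The 17.5% uses the linear risk over time assumed in Section 6.7: 3/12 × 10% + 9/12 × 20%.

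**4. Can the direction change?** Keep background risk at 20% in each arm overall, halve it in continuing INH participants, and give INH stoppers no protection.

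- *Lower-risk INH stoppers.* f = 20% in both arms, background risk 10% in INH stoppers and 20% in placebo stoppers. Continuing INH: (0.20 − 0.20·0.10)/0.80 × 0.5 = 11.25%. Analysed RR = 0.1125/0.20 = 0.56. All randomised: (0.80·0.1125 + 0.20·0.10)/0.20 = 0.55.
- *As above, placebo stoppers at 30%.* Continuing placebo: (0.20 − 0.20·0.30)/0.80 = 17.5%. Analysed RR = 0.1125/0.175 = 0.64, against 0.55 in all randomised. Efficacy is understated.
- *Higher-risk INH stoppers.* f = 20% on INH and 10% on placebo, background risk 30% in INH stoppers and 20% in placebo stoppers. Continuing INH: (0.20 − 0.20·0.30)/0.80 × 0.5 = 8.75%. Analysed RR = 0.0875/0.20 = 0.44. All randomised: (0.80·0.0875 + 0.20·0.30)/0.20 = 0.65.

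The sign depends on how stopper risk differs between arms.

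**The case against.** A reader might infer that stopping drug before month 6 automatically removes a participant from the trial. The text does not go that far. Withdrawal is permitted, not required; temporary interruptions count only once they total 90 days; the other-medicines ground depends on dose and the investigator's judgement. Section 6.5 says hepatotoxicity interrupts the intervention and leads to clinical care, without saying the participant leaves. The month-6 clause is also ambiguous: it may date the stopping or the offer of the choice. All of this stands. What remains is that no option to stay is stated for earlier stoppers, so retention is left to unplanned discretion.

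The partial-consent sentence in Section 6.6 may already secure a month-12 or month-24 IGRA for some early stoppers. It may equally fall under the six-month threshold that opens its paragraph. Either reading is open, so the sentence does not settle the matter.

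A reader might also take arm-specific stopping rates from the background sections. The documents do not support that. The only like-for-like pair in Section 2.5 is hepatitis of 0.52% on INH against 0.12% in controls: 0.4 percentage points, or about 1.5 of 364. The higher INH figures there (2.4%, 2.7%, and 6% on average) come from other sources and cannot be set against that 0.12%. The 83.8% and 69% quoted there are adherence rates in people with latent TB; they do not say how many stop, or when.

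Finally, the present intention-to-treat definition already excludes early stoppers, so the two issues overlap. They do, but mending the definition leaves the outcomes uncollected.

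**Conclusion.** The concern holds in a limited form. The plan permits withdrawal of participants who stop drug, states the off-drug follow-up option only from month 6, and plans no month-12 IGRA for those withdrawn earlier. That is inconsistent with Section 6.5 and with the claimed intention-to-treat basis, and Section 6.6 leaves the sampling of early stoppers unclear.

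Efficacy is likely to be overstated relative to an all-randomised estimate, because INH stoppers who lose protection drop out of the comparison. With 5% to 30% stopping early and no protection in INH stoppers, a relative risk reduction of 50% would correspond to 47.5% to 35% in all randomised. Those inputs are assumptions. There is no bias if stoppers keep the full effect, and the direction can reverse if stopper risks differ by arm, so it would be wrong to report overstatement, or any particular size, as established. Nor is every estimate beyond recovery: some exclusion-visit IGRAs may exist and sensitivity analyses remain possible, though neither replaces the month-12 result.

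This should be fixed; confidence is medium.

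**What to change.** In Section 6.4, state that stopping study drug at any time does not by itself end follow-up. Offer the existing stay-without-DOT option to all such participants who still consent and can be reached, with IGRA and sputum sought at whichever of the month 6, 12 and 24 visits remain. Handle transfer and release as feasible.

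Reconcile Section 6.5 and the partial-consent sentence in Section 6.6 with this, and let the intention-to-treat set include these participants; otherwise the results would be collected and then left out. Add a missing-data sensitivity analysis for those who still cannot be sampled.

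This concerns outcome collection only and changes no rule on when treatment is stopped.

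The cost is protocol wording, any matching consent wording, and some additional retained visits. Under the illustrative 5% to 30%, that is up to 0.05 × 364 ≈ 18 to 0.30 × 364 ≈ 109 participants per arm, each at visits already in the schedule. The documents contain no budget, so the expense cannot be stated. The observed effect may also be smaller; with all 364 per arm followed, power in the no-protection case stays above 90% at 5% and 10% early stopping and falls to 83.9% at 20% and 72.1% at 30%.

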## 6.5 Conducting the study

Participants will be invited to participate in the clinical trial through the consent process and will agree to participate in the study by signing the ICF.

In the recruitment interval, prior to any intervention, participants will respond to the AUDIT questionnaire - which assesses various levels of alcohol use, from safe use to likely dependence - and eligibility criteria will be checked. In the recruitment interval, participants will have a 9mL sample of peripheral blood collected for testing of IGRA (QuantiFERON® TB GOLD PLUS kit - Qiagen, HIV, hepatitis B (HBsAg) and C (Anti-HCV) and serum levels of liver enzymes (AST and ALT).

After the results of these initial tests (HIV, hepatitis B and C, IGRA, AST and ALT), if eligible, the participant will answer questionnaires containing socioeconomic, medical and criminal history and have a sample of sputum collected for culture.

The participant will be included in the study without the result of the culture and, in case of a positive result for Mtb, the intervention will be suspended, the same will be excluded from the study and treated according to the MS protocol. If the sputum culture is contaminated, a new sample should be collected within 30 days after the result.

The recruitment interval will last 20 to 45 days.

On the day of initiation of DOT (D0), each participant will receive a supervised dose (three oral tablets) of INH (900mg) or placebo. The same will happen twice a week for 12 months. During the DOT the participant will be asked about AE.

Blood samples will be collected every three months after D0 to measure hepatic enzyme levels (AST and ALT), as well as clinical evaluation and verification of AE, as shown in figure 1.

At six months and at the end of the intervention (12th month), all participants will have a sample of sputum collected for culture and a blood sample for detection / quantification of interferon gamma. The same evaluation will be repeated in the 24th month counted from D0, that is, one year after the end of the intervention.

At follow-up visits of 6, 12 and 24 months, if the interferon gamma result is indeterminate, the participant remains in the clinical trial and a new sample is collected within 30 days. If the IGRA result is positive (result standardized according to the package insert of the Qiagen®), the participant will suspend the medication (in the case of the 6-month visit), will be excluded from the study and treatment for latent TB.

If the sputum culture is positive for Mtb, the participant will be excluded from the study and treatment for active TB according to MS will be offered. If the sputum culture is contaminated, a new sample should be collected within 30 days after the result.

In the occurrence of hepatotoxicity, diagnosed through hepatic enzyme levels (elevation greater than five times the upper limit of the test if the individual is asymptomatic) and / or clinical examination (presence of jaundice, right upper quadrant pain, dark urine, fever, asthenia, myalgia), the intervention will be interrupted and the participant will be led to clinical care by the project team, according to the project's SOP. In this study, the following values will be used as laboratory parameter: AST: 8-40 IU / mL and ALT: 5-30 IU / mL(54,55). Other laboratory tests may be

requested from the research participants, according to the clinical judgment of the physician responsible for the care of the AE and according to the specific SOP of the project.

IGRA, smear culture, and serology for HIV, hepatitis B and C are performed LPCS / UFGD. The AST/ALT exams and other laboratory tests, when necessary, are performed in an external laboratory.

During the course of the study, the Notification of Injury Information System will be used to identify the occurrence of active TB cases in both groups.

The box below summarizes the activities to be developed at each stage of the protocol.

	Enrollment	DOT start (D0)	1 st visit (3 mo± 15 d)	2 nd visit (6 mo± 15 d)	3 rd visit (9 mo± 15 d)	4 th visit (12 mo± 30 d)	5 th visit (24 mo± 30 d)	Early exclusion visit
Consent process	X							
Verification of inclusion and exclusion criteria	X							
AUDIT	X							
Medical history	X							
Criminal history	X							
Randomization		X						
DOT star		X						
DOT end						X		
IGRA	X			X		X	X	(X)
ALT, AST	X		X	X	X	X		(X)
Another laboratory exams	(X)		(X)	(X)	(X)	(X)		(X)
Anti-HIV, HBsAg e Anti-HCV	X							(X)
Sputum coleccion	X			X		X	X	(X)
Clínical evaluation	X	X	X	X	X	X	X	X
Adverses events evaluation			X	X	X	X	X	X

DOT = Directly Observed Treatment, mo = months, d = days

Figura 1 - Schedule, second quarters, of research activities. The parentheses indicate that the procedures are optional.

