### **4.2 Specifics**

- Determine the impact of INH use on the incidence of active and latent TB in the prison population;
- To quantify the occurrence of adverse events, including hepatotoxicity, due to the use of INH;
- Evaluate residual protective effect until the 12th month after intervention;

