### **5.2 Secondary outcome**

Reduction of 50% in active TB in the treatment group after 12 months of intervention, estimated by sputum positive culture.

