#### 6.1.1 Sample and population of the study

This research will be carried out at one prison unit, located in the city of Dourados, in the state of Mato Grosso do Sul. Currently, this prison unit has approximately 2,300 inmates, with a mean age of  $31.5 \pm 9.4$  years; an average of  $9.7 (\pm 4.2)$  individuals per cell, who remain in a closed regimen, about  $20.8 (\pm 24.1)$  months. The TB indicators show a tuberculin test seroconversion rate of 26% (23-26) and incidence, 2.45 / 100,000(28).

The sample was calculated for a significance level of 5%, detection power of 90%, considering a percentage of occurrence of latent TB of 20% in the control group after one year of follow-up and 10% in the experimental group. For these parameters, 560 individuals will be needed for the study, however, 30% will be added for possible losses, ending the sample in 728 participants. Memory calculation available at <https://www.sealedenvelope.com/power/binary-superiority/>.

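### Section 6.5 excludes IGRA converters from the study, so active TB is undercounted in those most at risk and its absolute effect understated

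*Combined protocol and SAP*

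**What the plan says.** Section 6.5 takes the two tests together. At months 6 and 12 "all participants will have a sample of sputum collected for culture and a blood sample for detection / quantification of interferon gamma", and both are repeated at month 24. The exclusion rule applies "At follow-up visits of 6, 12 and 24 months": a participant with a positive IGRA "will be excluded from the study and treatment for latent TB". In Figure 1, sputum at the early exclusion visit is optional.

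The secondary outcome (5.2) is "Reduction of 50% in active TB in the treatment group after 12 months of intervention, estimated by sputum positive culture". A specific aim (4.2) is to "Evaluate residual protective effect until the 12th month after intervention". Section 6.5 adds that "the Notification of Injury Information System will be used to identify the occurrence of active TB cases in both groups" while the study runs. It does not say whether excluded participants are covered or whether their cases enter the analysis.

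Section 6.6 defines an active case by a positive smear or culture. It recognises seroconversion only at month 12 or 24. It plans a relative risk with its confidence interval, the relative and absolute risk reductions, and the NNT.

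Section 6.4 offers some participants another route. Those whose treatment is interrupted from month 6 onward, by their own decision or at medical discretion, may stay for all planned visits without the intervention.

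**The concern.** Section 2.1 describes latent infection as a state from which disease can later arise, so a new converter is at higher risk of active TB than a participant who is still uninfected. The rule stops scheduled cultures in exactly these people. If INH works as planned, more of them are on placebo. The loss is therefore related to both arm and outcome. At stake are the number of active-TB cases seen, the absolute risk reduction and the NNT. The documents do not say how excluded converters count in the active-TB numerator, denominator or person-years. A culture not taken cannot be recovered at analysis.

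**Working it through.** **Inputs from the protocol.** Section 6.1.1 gives 560 × 1.30 = 728, or 364 per arm. The two-proportion formula with continuity correction gives 572 in total, about 2% above 560, so the base figure is close enough to use. The rates are "latent TB of 20% in the control group after one year of follow-up and 10% in the experimental group". Section 6.7 assumes linear accrual, so the month-6 rates are 10% and 5%, as in the reference row of its table. The 2:1 ratio is a design assumption, not an observation.

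**Step 1: who loses which culture (converters = n × rate).**
- Month-6 converters lose the month-12 and month-24 cultures: 364 × 0.10 = 36.4 placebo, 364 × 0.05 = 18.2 INH; about 55 in all.
- All converters to month 12 lose the month-24 culture: 364 × 0.20 = 72.8 placebo, 364 × 0.10 = 36.4 INH; about 109 in all.
- With the 280 per arm before the loss allowance: 28 v 14, and 56 v 28.

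**Step 2: active TB missed to month 12.** The documents give no monthly progression rate. Assume 0.4% to 1% per month after infection, the same in both arms, with infections spread evenly, all detected at the next IGRA, no other case finding and no effect of latent-TB treatment. To first order, cases = infections × monthly rate × mean months since infection.
- Full follow-up (mean 6 months), at 0.4%: placebo 72.8 × 0.004 × 6 = 1.75; INH 36.4 × 0.004 × 6 = 0.87.
- Under the rule (two six-month windows, mean 3 months each): placebo 2 × 36.4 × 0.004 × 3 = 0.87; INH 2 × 18.2 × 0.004 × 3 = 0.44.
- Missed, month-6 converters over the next six months: placebo 36.4 × 0.004 × 6 = 0.87; INH 18.2 × 0.004 × 6 = 0.44. This is half in each arm.
- At 1% the counts are 2.5 times larger: placebo 4.37 to 2.18, INH 2.18 to 1.09.

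Allowing for depletion, the placebo figures become about 1.7 to 0.9 and 4.2 to 2.2. The missed share stays about half.

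**Step 3: effect measures at month 12.**
- Absolute risk reduction = 0.10 × rate × 6. At 0.4% it is 0.24 points and falls to 0.12; the NNT rises from 1/0.0024 = 417 to 1/0.0012 = 833. At 1% it falls from 0.60 to 0.30 points; the NNT rises from 167 to 333.
- Relative risk if all disease arises in converters: 0.87/1.75 = 0.50 with full follow-up and 0.44/0.87 = 0.50 under the rule.
- Relative risk with an assumed 0.2% per year of disease outside detected conversion, adding 364 × 0.002 = 0.73 cases per arm, at 0.4% per month: (0.87 + 0.73)/(1.75 + 0.73) = 0.65, moving to (0.44 + 0.73)/(0.87 + 0.73) = 0.73.
- With 0.5% per year (1.82 cases per arm) it moves from 0.76 to 0.84.

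**Step 4: allowing for latent-TB treatment.** Section 2.5 cites a relative risk of 0.40 for INH prophylaxis. Applied, crudely, to all later disease in converters, the cases that would occur on placebo are 0.87 + 0.40 × 0.87 = 1.22, of which the rule shows 0.87. The missed share is then 0.35/1.22 = 29% rather than half.

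**Step 5: month-6 converters and the latent-TB count.** Section 6.5 excludes a month-6 converter, who then has no month-12 or month-24 IGRA. Section 6.6 recognises conversion only at those two visits. Read literally, month 12 would count 72.8 − 36.4 = 36.4 placebo and 36.4 − 18.2 = 18.2 INH events, half of those expected.

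**The case against.** Several stronger readings are tempting, and the documents do not support them.

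- *The secondary outcome is biased towards no effect.* This is not automatic for the planned relative risk. A 2:1 loss on a 2:1 risk leaves 0.50 at 0.50. A shift needs disease outside detected conversion, at a rate that the documents do not give.
- *Month-12 exclusions also harm outcome 5.2.* They do not. IGRA and sputum are taken at the same visit, so month-12 converters have already given that culture. They lose only month 24.
- *Most active TB falls in people no longer followed.* Applying the 5-10% reactivation in section 2.1 to every converter mixes time scales, because that figure refers to disease after a few years.
- *The exclusion rule spoils the residual-effect comparison.* A converter cannot convert again, so new conversions in months 12-24 can only be compared among month-12 negatives under any rule. That comparison is selected by arm, but retaining converters would not change it.
- *Half the primary events are discarded.* Section 6.1.1 counts occurrence over a year and section 6.7 uses month-6 results, so the wording in 6.6 is an ambiguity to settle, not a stated intention.

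Existing provisions also help. Notification surveillance is planned in both groups, and the case definition in 6.6 does not require a study culture. Sputum may be taken at the exclusion visit, and 6.4 already has a retention route. These mitigate the problem but do not close it. Cover for excluded participants is not stated, notification would miss cases that only scheduled sputum would find, and 6.5 does not connect to the route in 6.4.

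Finally, retained converters would still be treated for latent TB, which itself narrows the contrast. That stands, and it limits what the fix can recover.

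**Conclusion.** The concern holds as an arm-related and outcome-related loss of follow-up. On design rates, about 36 v 18 participants lose the month-12 culture and about 73 v 36 the month-24 culture. Active TB is undercounted, more on placebo in absolute terms. With no other case finding, about half of infection-related cases to month 12 are missed if latent-TB treatment has no effect, and about 29% if it acts as in step 4. The absolute risk reduction shrinks by the same share; in the first case the NNT doubles. The progression and background rates are assumptions. A relative risk biased towards 1 is possible but not established.

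This is a cheap improvement rather than an essential correction. The outcome is secondary, the sample size was not calculated for it, and the primary IGRA endpoint is reached before exclusion. The wording in 6.6 on month-6 converters should be settled in the same edit.

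**What to change.** - Reconcile 6.5 with the retention option in 6.4. After a positive IGRA the latent-TB endpoint is reached, and the participant stays in outcome follow-up for the month-12 and month-24 clinical and sputum visits. Medication and latent-TB care remain as the protocol states.
- Make the same exception in the withdrawal list in 6.4. It allows withdrawal when an exclusion criterion arises during follow-up, and a reactive IGRA is one in 6.3.
- State that the notification search covers every randomised participant to month 24, whatever their study status, and that notified cases meeting the 6.6 definition count.
- Analyse active TB by randomised arm, and report latent-TB treatment after conversion.
- In 6.6, count month-6 converters as events in cumulative conversion to months 12 and 24. Label the month 12-24 comparison among IGRA-negative participants as descriptive.

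**Cost.** About 55 people keep a month-12 visit and about 110 a month-24 visit, all already scheduled. Treatment of converters, mostly on placebo, still dilutes the contrast, possibly substantially. On the step 4 assumptions at 0.4% per month, the change recovers only about 0.35 placebo cases (0.40 × 0.87) and 0.17 INH cases (0.40 × 0.44) to month 12. The report should say that the active-TB result estimates the effect of INH under a policy of treating converters.
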